# 8 EVALUATION DURING STUDY

- 8.1 Complete history and physical examination including ECOG performance status, vital signs, and weight at study drug initiation and every 3 weeks (±1 week) thereafter during the study.
- 8.2 CBC and differential at least 1-2 times per week (differential not required if total WBCs  $\leq 0.5 \times 10^9$ /L).
- 8.3 CMP (defined below in study calendar) at least weekly.
- 8.4 EKG on day 10.
- 8.5 Blood cultures if patient develops fever (oral temperature  $\geq 100.4$  °F or 38 °C sustained over a 1-hour period or a single oral temperature measurement of  $\geq 101$  °F or 38.3 °C).
- 8.6 Chest x-ray (CXR) if patient develops neutropenic (ANC <500/mm^3) fever or any sign or symptom of pulmonary infection (lungs or sinus).
- 8.7 CT scan of the chest (± sinus) within 3 (±1) days of development of neutropenic fever or any sign or symptom of respiratory infection. If positive for infection, CT chest (±sinus) needs to be repeated 2 weeks after institution of therapeutic antimicrobials and then as per physician discretion until resolution of the infection.
- 8.8 Iron staining of bone marrow at the time of response assessment for AML/MDS. Failure to perform this will not be considered a protocol deviation or violation.
- 8.9 Plasma isavuconazole levels on day 8 and day 15 just prior to dosing.
- 8.10 Antimicrobial susceptibility testing of fungal isolates from any IFIs that may develop during the course of the study.
- 8.11 Patients that come off therapy will continue follow-up for toxicity (clinic visit or telephone interview) for 30 days (+/- 5 days) after the end of therapy. At the end-of-study visit, patients will have a physical examination, including recording of vital signs, weight and assessment of ECOG performance status, a CBC, CMP, and AE evaluation.
- 8.12 All study participants will be given a study drug diary to keep a log of each dose of study drug taken, the time the dose was taken, and any missed doses along with the reason for missing the dose, as well as doses that may be vomited up.

#### **Concomitant medications**

- a) All patients may also receive standard antibacterial and antiviral prophylaxis.
- b) No concomitant antifungal therapy is allowed while patients are receiving study drug.
- c) Co-administration of strong CYP3A4 inducers or inhibitors is contraindicated.
- d) Concomitant medications will be entered in the medical record, not the case report form.

	Pre- Study*	Wk 1	Wk 2	Wk 3	Wk 4	Wk 5	Wk 6	Wk 7	Wk 8	Wk 9	Wk 10	Wk 11	Wk 12	Off Study f
Isavuconazonium sulfate		А	А	А	А	А	А	А	А	А	А	А	А	
Informed consent	Х													
Demographics	Х													
Medical history c	Х	х			Х			х			Х			
Concurrent meds	Х	X											X	
Physical exam c	Х	Х			Х			х			Х			Х

#### STUDY CALENDAR

Vital signs	Х	х			Х			Х			Х			Х
Height	Х													
Weight	Х	Х			Х			Х			Х			Х
Performance status	Х	х			Х			х			Х			Х
CBC w/diff, plts (at least 1-2 times per week during study) g	Х	Х	Х	Х	х	Х	Х	Х	Х	Х	Х	Х	х	Х
CMP a at least weekly	Х	х	Х	Х	Х	х	х	х	Х	Х	Х	Х	х	Х
EKG (baseline and day 10)	Х		Х											
Adverse event evaluation		X											X	Х
Chest x-ray	Х	If any fever	If any sign or symptom of pulmonary infection or neutropenic (ANC < 500/mm  ) fever develops.											
CT scan of chest (±sinuses)	X b	Withi or syn	Within 3 ( $\pm$ 1) days of development of neutropenic (ANC <500/mm  ) fever or any sign or symptom of respiratory infection (lungs or sinus).											
Blood cultures		If patient develops fever (single oral temp $\geq 101^{\circ}$ F (38.3°C) or oral temp $\geq 100.4^{\circ}$ F (38°C) sustained x 1 hour).												
Iron staining of bone marrow	Х	When	Whenever bone marrow is sampled for assessment of disease status of AML/MDS.											
ß-HCG	X d													
Isavuconazole levels e			Х	Х										
Antimicrobial susceptibility testing of fungal isolates	Any time a breakthrough fungal infection occurs and a sample is available for fungal culture.													

 
*Within 1 week prior to study treatment initiation.
 
A: Isavuconazonium sulfate: 372 mg (200 mg of isavuconazole) daily.
 
a: Albumin, alkaline phosphatase, total bilirubin, bicarbonate, BUN, calcium, chloride, creatinine, glucose, LDH, phosphorus, potassium, total protein, SGOT [AST], SGPT [ALT], sodium.
 
b: Only if patient is febrile and/or presents with signs/symptoms of respiratory infection (lungs or sinus).
 
c: ±1 week.
 
														

Serum or urine pregnancy test (women of childbearing potential). d:

e: On days 8 and 15 (before the day's dose).

Off-study evaluation (clinic visit or telephone interview). Differential not required if total WBCs  $\leq$  0.5 x 10^9/L. f:

g:

#### 9 **ASSESSMENT OF EFFICACY**

# 9.1 EORTC/MSG criteria for proven IFIs

Fulfillment of any of these criteria represents a proven IFI.

Analysis and specimen	Molds a	Yeasts a
Microscopic analysis: sterile material	Histopathologic, cytopathologic, or direct microscopic examination b of a specimen obtained by needle aspiration or biopsy in which hyphae or melanized yeast-like forms are seen accompanied by evidence of associated tissue damage	Histopathologic, cytopathologic, or direct microscopic examination b of a specimen obtained by needle aspiration or biopsy from a normally sterile site (other than mucous membranes) showing yeast cells—for example, Cryptococcus species indicated by encapsulated budding yeasts or Candida species showing pseudo-hyphae or true hyphae c
Culture		
Sterile material	Recovery of a mold or "black yeast" by culture of a specimen ob- tained by a sterile procedure from a normally sterile and clini- cally or radiologically abnormal site consistent with an infectious disease process, excluding bronchoalveolar lavage fluid, a cranial sinus cavity specimen, and urine	Recovery of a yeast by culture of a sample obtained by a sterile procedure (including a freshly placed [<24 h ago] drain) from a normally sterile site showing a clinical or radiological abnormality consistent with an infectious disease process
Blood	Blood culture that yields a mold d (e.g., Fusarium species) in the context of a compatible infectious disease process	Blood culture that yields yeast (e.g., Cryptococcus or Candida spe- cies) or yeast-like fungi (e.g., Trichosporon species)
Serological analysis: CSF	Not applicable	Cryptococcal antigen in CSF indicates disseminated cryptococcosis

a If culture is available, append the identification at the genus or species level from the culture results.

b Tissue and cells submitted for histopathologic or cytopathologic studies should be stained by Grocott-Gomorri methenamine silver stain or by periodic acid Schiff stain, to facilitate inspection of fungal structures. Whenever possible, wet mounts of specimens from foci related to invasive fungal disease should be stained with a fluorescent dye (e.g., calcofluor or blankophor).

c Candida, Trichosporon, and yeast-like Geotrichum species and Blastoschizomyces capitatus may also form pseudohyphae or true hyphae.

d Recovery of Aspergillus species from blood cultures invariably represents contamination.

#### 9.2 EORTC/MSG criteria for probable and possible IFIs

At least one host factor, one clinical feature and one form of mycological evidence are required for a diagnosis of "probable" IFI, as defined in the table below.

A "possible" IFI is defined by the presence of appropriate host factors and sufficient clinical evidence consistent with IFI but without any mycological support.

Host factorsa Recent history of neutropenia (<0.5 × 10^9 neutrophils/L [<500 neutrophils/mm^3] for >10 days) temporally related to the onset of fungal disease Receipt of an allogeneic stem cell transplant Prolonged use of corticosteroids (excluding among patients with allergic bronchopulmonary aspergillosis) at a mean minimum dose of 0.3 mg/kg/day of prednisone equivalent for >3 weeks Treatment with other recognized T cell immunosuppressants, such as cyclosporine, TNF-a blockers, specific monoclonal antibodies (such as alemtuzumab), or nucleoside analogues during the past 90 days Inherited severe immunodeficiency (such as chronic granulomatous disease or severe combined immunodeficiency) Clinical criteriab Lower respiratory tract fungal diseasec The presence of 1 of the following 3 signs on CT: Dense, well-circumscribed lesions(s) with or without a halo sign Air-crescent sign Cavity Tracheobronchitis Tracheobronchial ulceration, nodule, pseudomembrane, plaque, or eschar seen on bronchoscopic analysis Sinonasal infection Imaging showing sinusitis plus at least 1 of the following 3 signs: Acute localized pain (including pain radiating to the eye) Nasal ulcer with black eschar Extension from the paranasal sinus across bony barriers, including into the orbit CNS infection 1 of the following 2 signs: Focal lesions on imaging Meningeal enhancement on MRI or CT Disseminated candidiasisd At least 1 of the following 2 entities after an episode of candidemia within the previous 2 weeks: Small, target-like abscesses (bull's-eye lesions) in liver or spleen Progressive retinal exudates on ophthalmologic examination Mycological criteria Direct test (cytology, direct microscopy, or culture) Mold in sputum, bronchoalveolar lavage fluid, bronchial brush, or sinus aspirate samples, indicated by 1 of the following: Presence of fungal elements indicating a mold Recovery by culture of a mold (e.g., Aspergillus, Fusarium, Zygomycetes, or Scedosporium species) Indirect tests (detection of antigen or cell-wall constituents)e Aspergillosis Galactomannan antigen detected in plasma, serum, bronchoalveolar lavage fluid, or CSF Invasive fungal disease other than cryptococcosis and zygomycoses  $\beta$ -p-glucan detected in serum NOTE. Probable IFD requires the presence of a host factor, a clinical criterion, and a mycological criterion. Cases that meet the criteria for a host factor and a clinical criterion but for which mycological criteria are absent are considered possible IFD. a Host factors are not synonymous with risk factors and are characteristics by which individuals predisposed to invasive fungal diseases can be recognized. They are intended primarily to apply to patients given treatment for malignant disease and to recipients of allogeneic hematopoietic stem cell and solid-organ transplants. These host factors are also applicable to patients who receive corticosteroids and other T cell suppressants

b Must be consistent with the mycological findings, if any, and must be temporally related to current episode.

c Every reasonable attempt should be made to exclude an alternative etiology.

as well as to patients with primary immunodeficiencies.

d The presence of signs and symptoms consistent with sepsis syndrome indicates acute disseminated disease, whereas their absence denotes chronic disseminated disease.

e These tests are primarily applicable to aspergillosis and candidiasis and are not useful in diagnosing infections due to *Cryptococcus* species or Zygomycetes (e.g., *Rhizopus, Mucor*, or *Absidia* species). Detection of nucleic acid is not included, because there are as yet no validated or standardized methods.

# **10 CRITERIA FOR REMOVAL FROM THE STUDY**

Patients will be removed from the study if:

- 12 weeks have elapsed from the start of therapy, or
- The ANC has recovered to ≥0.5 x 10^9/l and CR with or without complete count recovery has been documented (per ELN criteria), or
- A proven or probable IFI has occurred (as defined by the EORTC/MSG), or
- Unacceptable drug toxicity develops, or
- The patient or investigator decide to withdraw the patient from the study, or
- Patient dies while on study.

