# 4.2 ENDPOINTS

# 4.2.1 Primary

4.2.1.1 Incidence of proven or probable IFI (by EORTC/MSG criteria) during the first 100 days from initiation of isavuconazole prophylaxis.

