# 6.2 Duration of prophylaxis

Study drug treatment will be administered daily continuously until, whichever occurs first:

- recovery from neutropenia (ANC  $\geq 0.5 \times 10^9/L$ ) and attainment of complete remission (CR), with or without complete count recovery or
- occurrence of a proven or probable IFI as defined by EORTC/MSG criteria, or
- 12 weeks have elapsed from the start of therapy, or
- development of unacceptable toxicity, or
- patient's withdrawal from the study (patient or investigator decision), or

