#### 6.5 Long-term follow-up

The Long-Term Follow-Up schedule begins at the end of treatment assessment and continues until death. All patients who receive at least one dose of study drug will be followed for survival every 6-12 months by telephone call to patient, family, local physician, surface or electronic mail. All patient follow up will continue under DR09-0223. A separate informed consent for that study will be required. Patients may be removed from this current protocol and followed up on the DR09-0223 after completing all protocol related assessments.

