# **11 STATISTICAL CONSIDERATIONS**

This is an open label, phase II clinical trial to evaluate the efficacy of isavuconazole prophylaxis in adult patients with newly diagnosed AML/MDS and neutropenia. A total of 100 patients will be accrued from M.D. Anderson Cancer Center (MDACC), at a rate of 5 patients per month. The primary endpoint is the incidence of proven or probable invasive fungal infections (IFI) for up to 100 days from prophylaxis initiation. Occurrence of IFIs will be assessed during the period of prophylaxis (see section 6.2) and up to 100 days from prophylaxis initiation.

The method of Thall, Simon and Estey will be used for futility and toxicity monitoring in this study.

A 10% frequency of IFIs is observed in general in AML during remission induction. The current standard of care is posaconazole prophylaxis in preventing IFI. Assuming that isavuconazole is as effective as posaconazole, subjects receiving isavuconazole would be expected to have a 5% rate of IFIs. We assume a priori for IFI rate, p (IFI) ~ beta (0.1, 1.9). The following futility stopping rule will be applied in cohort sizes of 10, starting from the 10th patient: the trial will be stopped if Pr(p(IFI) > 0.05 | data) > 0.87. That is, we will stop the trial for new patient enrollment if at any time during the study we determine that there is a more than 87% chance that the IFI rate is more than 5%. Stopping boundaries corresponding to the IFI monitoring rule are shown in Table 1 below. The operating characteristics for the monitoring are summarized in Table 2. Multe Lean Desktop (version 2.1) was used to generate the IFI stopping boundaries and the OC table. We will submit a futility/toxicity summary to the IND Office Medical Monitor, after the first ten patients have completed study therapy, or administration is discontinued, whichever comes first; and every ten patients thereafter.

Number of patients	No. of patients with IFIs that will lead to the trial being stopped
10	2-10
20	3-20
30	4-30
40-50	5-50
60	6-60

Table 1. IFI stopping boundaries in cohort sizes of 10.

70-80	7-80
90	8-90

Table 2. Operating characteristics for IFI monitoring in cohort sizes of 10 (max sample size = 100).

True IFI rate	Prob(stop the trial	Average sample
	early)	size
0.01	0.005	99.6
0.02	0.02	98.1
0.03	0.06	95.3
0.04	0.13	90.9
0.05	0.23	84.9
0.06	0.35	77.7
0.07	0.48	69.8
0.08	0.60	61.8
0.09	0.71	54.2
0.1	0.80	47.3
0.15	0.98	25.5

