- Unless otherwise noted, the electronic SAE application (eSAE) will be utilized for safety reporting to the IND Office and MDACC IRB.
- SAEs will be captured from the time of the first protocol-specific intervention, until 30 days after the last dose of drug, unless the participant withdraws consent. SAEs must be followed until clinical recovery is complete and laboratory tests have returned to baseline, progression of the event has stabilized, or there has been acceptable resolution of the event.
- Additionally, any SAEs that occur after the 30 day time period that are related to the study treatment must be reported to the IND Office. This may include the development of a secondary malignancy.

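### The primary endpoint runs to day 100, but patients who stop study drug before about day 70 leave the study with no scheduled check of IFI status up to day 100

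*Combined protocol and SAP*

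**What the plan says.** - **Endpoint.** Section 4.2.1 counts proven or probable IFI "during the first 100 days from initiation of isavuconazole prophylaxis". Section 11 adds: "Occurrence of IFIs will be assessed during the period of prophylaxis (see section 6.2) and up to 100 days from prophylaxis initiation". Neither names a visit, contact, form or method for the period after drug stops.
- **End of drug.** Section 6.2: "Study drug treatment will be administered daily continuously until, whichever occurs first" of six events: neutrophil recovery with complete remission (CR), IFI, 12 weeks, unacceptable toxicity, withdrawal, death.
- **End of study.** Section 10: "Patients will be removed from the study if" one of the same six events occurs.
- **After drug stops.** Section 8.11: "Patients that come off therapy will continue follow-up for toxicity (clinic visit or telephone interview) for 30 days", give or take 5 days. The end-of-study visit consists of examination, vital signs, weight, performance status, CBC, CMP and AE evaluation. The study calendar runs from week 1 to week 12 plus one off-study column and has no day-100 entry.
- **SAEs (section 12).** Capture runs to 30 days after the last dose. Beyond that, "any SAEs that occur after the 30 day time period that are related to the study treatment must be reported", which does not cover an infection judged unrelated to the drug.
- **Long term (section 6.5).** Survival contact every 6-12 months under a different protocol with separate consent, to which patients may move "after completing all protocol related assessments".
- **Analysis (section 11, Analysis Plan).** The IFI rate is estimated with an exact 95% confidence interval. No denominator is given, and no rule for patients whose follow-up ends before day 100.

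**The concern.** The protocol treats leaving study drug and leaving the study as one event, while its primary endpoint needs status at a fixed time after the start of prophylaxis. Stopping at remission with count recovery is a planned route off drug. Section 1.1 gives CR rates of 60-85% in younger adults and 40-60% in elderly patients, so the affected group may be large, although the timing of CR is not stated. The primary objective covers successive cycles of therapy, so the uncovered period can include later neutropenic cycles.

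For early leavers the endpoint would rest on whatever happens to be in the chart. If they remain in the denominator as IFI-free, the error has one direction: the recorded rate can only be too low. The futility rule counts the same events, so it becomes less likely to stop a trial whose true rate is unacceptable. The secondary incidences of invasive aspergillosis and of other IFIs use the same 100-day window and have the same defect.

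**Working it through.** **1. The plan's own figures.** With the beta(0.1, 1.9) prior, the boundary at n patients is the smallest x for which Pr(p > 0.05) under beta(0.1 + x, 1.9 + n − x) exceeds 0.87. This gives 2, 3, 4, 5, 5, 6, 7, 7, 8 at n = 10, 20, …, 90, matching Table 1 at all nine looks. An exact binomial recursion over those looks (maximum 100) gives early-stopping probabilities of 0.226 at a 5% rate, 0.604 at 8% and 0.804 at 10%. Table 2 prints 0.23, 0.60 and 0.80. The design figures are sound if every IFI is counted.

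**2. The gap, from the documents alone.** The last scheduled contact is at day t + 30, where t is the day drug stops. Days without scheduled ascertainment = 100 − (t + 30) = 70 − t.

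| Drug stops (day) | Last contact (day) | Uncovered days |
|---|---|---|
| 28 | 58 | 42 |
| 35 | 65 | 35 |
| 42 | 72 | 28 |
| 70 | 100 | 0 |
| 84 (12 weeks) | 114 | none |

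With the ±5-day window the break-even point is day 65 to 75. Patients removed because of an IFI already have their endpoint. The gap therefore concerns those who stop for remission, toxicity or withdrawal.

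**3. Illustration of the effect.** None of these assumptions is in the documents, except that section 11 gives 10% as the IFI frequency during remission induction (not over 100 days):
- true 100-day rate p = 0.10, with constant hazard λ = −ln(0.90)/100 = 0.001054 per day;
- a fraction f of patients stops at day t;
- IFIs are captured up to the 30-day contact and none later;
- early leavers stay in the denominator.

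Recorded rate = f × [1 − exp(−λ(t + 30))] + (1 − f) × 0.10.

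- f = 0.6, t = 35: 0.6 × 0.0662 + 0.4 × 0.10 = 7.97%. Early stopping 0.600.
- f = 0.7, t = 28: 0.7 × 0.0593 + 0.3 × 0.10 = 7.15%. Early stopping 0.497.
- f = 0.4, t = 42: 0.4 × 0.0731 + 0.6 × 0.10 = 8.92%. Early stopping 0.71.

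The comparison value with full ascertainment is 0.80.

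**4. Milder and harsher cases.**
- *Front-loaded risk.* If only 10% of early leavers' IFIs fall after the 30-day contact, the recorded rate is 10% × (1 − 0.10f): 9.4% at f = 0.6 (9.6% at f = 0.4, 9.3% at f = 0.7). Early stopping at 9.4% is 0.753.
- *Many early stops.* If 85% stopped at day 28, the missed share on a straight-line approximation is 0.85 × 42/100 = 0.357. The recorded rate is 10% × 0.643 = 6.43%, and early stopping is 0.40.

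**The case against.** The strongest reply is that removal under section 10 should be read as coming off drug. Section 11 commits to assessment up to day 100 without limiting it to patients on drug, and section 6.5 allows transfer only "after completing all protocol related assessments". On that reading the assessment is still owed, and only a calendar row is missing. The intention is indeed there. But no day-100 check appears among the assessments to be completed, and section 10 says the patient has left the study.

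A second reply is that IFI detection is event-driven throughout: cultures on fever, and CT on neutropenic fever or respiratory signs. No calendar row is an IFI assessment even during weeks 1-12. That is true, but section 8 prescribes those procedures for evaluation during the study. By the same argument the 30-day contact has no IFI item of its own, so coverage in those 30 days rests on AE and SAE reporting. The day-70 cut-off still has a basis in the text, because SAE capture narrows to treatment-related events at 30 days.

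A third reply is that the Analysis Plan uses Kaplan-Meier for time-to-event outcomes, and time to IFI diagnosis is one of them. Censoring there deals with incomplete follow-up in a secondary analysis. It does not settle the primary proportion.

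The criticism of the size does stand. The share stopping early, the hazard shape and zero later capture are all assumed. A single centre giving successive cycles may find many late cases in its own charts, and the front-loaded case shows only a small effect.

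**Conclusion.** The concern holds and should be fixed before the primary result is relied on. For patients who stop drug before about day 70, the scheduled procedures do not determine the primary endpoint as defined. This follows from the text and from 100 − 30 = 70, and needs no outside assumption. The direction is also clear: if events are missed and these patients stay in the denominator, the recorded rate is too low and the futility rule is weakened. The amount is not identifiable from the documents. In the main illustration a true 10% rate is recorded as about 8.0%, with early stopping at 0.60 instead of 0.80. Front-loaded risk reduces the loss to about 0.05 (0.75 against 0.80), and very frequent early stopping would increase it. The case for correction does not depend on which of these applies.

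**What to change.** 1. **Reconcile sections 4.2.1, 6.5, 8.11, 10 and 11** by defining leaving study drug and leaving the study separately. Keep every treated patient under observation for IFI status until day 100, death or withdrawal of consent. The rules for stopping drug need no change. The consent text was not available for review, so confirm that it covers this contact.
2. **Add a day-100 row to the study calendar**, for example ±7 days, by telephone or chart review. Record any IFI with its date and EORTC/MSG class, systemic antifungal use, and vital status.
3. **In the Analysis Plan, state the denominator** of the primary rate and the handling of death or loss before day 100. One option is a cumulative incidence with death as a competing event, reported beside the exact-interval proportion.
4. **State which IFI window each futility look counts.** The monitoring summaries are triggered when patients complete or discontinue therapy, not at day 100.

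The cost is wording plus one telephone or chart check per patient, at most 100, at a single centre. Sample size, stopping boundaries and Table 2 stay as printed.
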